3.2 Discussion of design

The design for the present trial is based on the recommendation from the EMA guideline on the clinical development of products for AIT for the treatment of allergic diseases (EMEA 2008), as recommended in the WHO position paper on AIT for development of SLIT (Bousquet et al. 1998), and based on the experience from previous ALK trials with AIT.

The primary endpoint TCS is the sum of the average rhinoconjunctivitis DSS and the average DMS during the 2nd PGPS. The primary endpoint analysis is from the peak grass pollen season in order to minimise the effect of natural variation that exists over the entire grass pollen season. As symptom-relieving medications are allowed in the trial, it is reasonable to adjust the reported symptom score to account for the symptom-relieving medications used, in order to get a more accurate representation of symptomatology.

Scientific recommendations for ARC trials currently describe a primary outcome reflecting a combined symptom and medication score severity with secondary outcome measures including validated symptom scores and/or health related QoL questionnaires (Pfaar et al. 2014). However, in order to make additional claims on QoL, hierarchical testing will be employed on this trial with efficacy endpoints including symptom and medication scores and RQLQ QoL scores.

The symptom score has been designed based on EMA guidance documentation (EMEA 2008) and on scoring from previous and ongoing ALK trials. The medication score proposed for this trial has been used in numerous clinical trials performed with the authorised products GRAZAX[®]/GRASTEK[®] and RAGWITEK[®] (Blaiss et al. 2011) (Nelson et al. 2011) (Creticos et al. 2013) (Maloney et al. 2014) and was developed by the sponsor based on recognised guidelines (EMEA 2008) (Canonica et al. 2007), as well as on thorough discussions with key opinion leaders and specialists within the field of allergy.

Clinical development experience with grass AIT has shown that the treatment effect during the first PGPS is strongly linked to the duration of the pre-seasonal exposure to AIT. Results from clinical

Clinical trial protocol	Date:	12-Nov-2021	
Trial ID: SU-G-01	Version:	4.0	
EudraCT No. 2020-000455-12	Status:	Final	
CONFIDENTIAL	Page:	27 of 77	

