15.2 Sample size and power considerations

General considerations:

In this trial, primary and secondary endpoints are tested hierarchically to control the family-wise error rate at 5% level. Individual endpoint analyses are based on treatment comparisons using a 2-sided t-test on a 5% level of significance.

The power calculations were done in two steps. The initial sample size calculation was done for observed cases only. This sample size is then evaluated using the estimand framework. The power is calculated for both the primary endpoint (TCS) and the key secondary endpoint (RQLQ). It is expected that the treatment difference in RQLQ is greater than the minimal clinically important difference (MCID) (0.16).

TCS power calculation:

The estimated TCS mean, standard deviation and treatment differences during the peak season from three trials is presented in **Table 8**. The power calculation is based on a TCS treatment difference of 21% (1.64 in absolute value) and a common standard deviation of 5.5. Under these assumptions, the trial has a power of 80% with the sample size of 180 evaluable subjects. The power will be 86% for the primary estimand and 80% for the secondary estimand with the assumption that 10% out of 220 subjects will discontinue the trial, with 4.5% of subjects discontinuing due to adverse events and 1% due to lack of efficacy each year.

Table 8	Mean and standard deviation of TCS during the peak of a season.
---------	---

Trial	Placebo μ (σ)	Active μ (σ)	Difference Absolute (relative)
GT-08 2006	8.44 (5.48)	5.14 (4.06)	3.3 (39%)
P05238	7.74 (6.50)	6.10 (5.09)	1.64 (21%)
P08067	5.73 (5.03)	4.56 (4.60)	1.17 (20%)
Average			2.04

RQLQ power evaluation:

The estimated RQLQ mean, standard deviation and treatment differences during the peak season from 3 trials raw data is presented in **Table 9**.

Table 9Mean and standard deviation of RQLQ during the peak of a season.

Trial	Placebo	Active	Difference
	μ (σ)	μ (σ)	Absolute (relative)
GT-08 2005	1.82 (1.11)	1.37 (0.97)	0.45 (25%)

Clinical trial protocol	Date:	12-Nov-2021	ALK
Trial ID: SU-G-01	Version:	4.0	
EudraCT No. 2020-000455-12	Status:	Final	
CONFIDENTIAL	Page:	59 of 77	

GT-08 2006	1.48 (1.05)	1.05 (0.91)	0.43 (29%)
P05238	1.73 (1.34)	1.41 (1.12)	0.33 (18%)
P08067	1.32 (1.11)	1.18 (1.08)	0.15 (11%)
Average			0.34

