A common standard deviation of 1.15 has been assumed in the power evaluation. An expected placebo mean is 1.60 and an expected treatment difference is 0.34. With 180 evaluable subjects per treatment arm, the power of 93% is reached for testing if RQLQ treatment difference is greater than proposed MCID of 0.16. The power will be 95% for the primary and 92% secondary estimands for the sample size of 220 subjects with the same discontinuation assumptions as for TCS.

Conclusion:

The suggested sample size is 180 evaluable subjects per treatment arm. 220 subjects should be randomised in each arm, assuming a 10% discontinuation of subjects per year, where 1% discontinued due to lack of efficacy and 4.5% due to adverse events. In such case, the trial will have a power of at least 80% in order to detect a statistically significant difference of at least 21% with common standard deviation no larger than 5.5 for primary endpoint in observed case scenario. The trial will have a power of 86% and 80% for primary endpoint for primary and secondary estimands respectively. The trial will have a power of at least 93% to detect treatment difference greater than 0.16 in RQLQ for observed case. Similarly, 95% and 92 % for the primary and secondary estimand respectively.

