15.10 Multiplicity

The trial product estimand is the primary estimand for all endpoints. The analyses for the main estimators will be controlled for multiplicity to ensure a family wise type I error rate is no lager than 5%. The multiplicity will be controlled by employing hierarchical testing: pre-specifying the order of the hypothesis to be tested. For all 4 endpoints the null hypothesis tested is the hypothesis of equality of placebo and 5-grass mix SLIT-drops treatment group.

The order of hypothesis to be tested is:

- 1. The primary endpoint is the average daily allergic rhinoconjunctivitis total combined score (TCS) during 2nd PGPS.
- 2. The overall RQLQ score during the 2nd PGPS
- 3. The average daily allergic rhinoconjunctivitis TCS during the 1st PGPS
- 4. The overall RQLQ score during the 1st PGPS

The primary endpoint is the first hypothesis in the hierarchy and will be tested on a 5% significance level. The endpoints from 2nd to 4th in hypothesis tests will be only carried out if all previously tested hypotheses are statistically significant at the 5% level.

Additional endpoints and analyses are supportive in nature and will not be controlled for multiplicity.

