15.11.3 Handling of intercurrent events and missing data for the treatment policy estimand

For subjects discontinuing trial treatment, all diary data (including data collected after discontinuation of trial treatment) will be included in the derivation of the primary endpoint (see Section **15.1.3**). Subjects for whom the primary endpoint is missing will be included in the analysis through multiple imputation as follows:

 For subjects discontinuing trial treatment due to treatment-related AEs or lack of efficacy, multiple imputation of the missing endpoint will be from the placebo group. This assumes that missing data following treatment-related discontinuation of trial treatment is MNAR and that subjects no longer taking active treatment for these reasons would have shown similar efficacy to subjects receiving placebo.

Clinical trial protocol	Date:	12-Nov-2021	
Trial ID: SU-G-01	Version	4 0	
EudraCT No. 2020-000455-12	Status:	Final	
CONFIDENTIAL	Page:	64 of 77	

• For subjects discontinuing trial treatment due to non-treatment related reasons, multiple imputation of the missing endpoint will be their own treatment group. This assumes that the missing data are MAR.

The sensitivity estimator for the treatment policy estimand will use multiple imputation from the placebo group for all subjects that discontinue trial treatment regardless of the reason for discontinuation. Further sensitivity estimator(s) for the treatment policy estimand may also be considered and will be detailed in the SAP.

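### The stated RQLQ power (93% in the protocol, 98% in the SAP) is the chance that the estimate exceeds the MCID; the planned test has about 80%

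*Protocol*

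**What the plan says.** Protocol section 15.2 assumes an RQLQ difference of 0.34 and a common SD of 1.15. At 180 evaluable subjects per arm it states that "the power of 93% is reached for testing if RQLQ treatment difference is greater than proposed MCID of 0.16", and its conclusion repeats: "The trial will have a power of at least 93% to detect treatment difference greater than 0.16 in RQLQ for observed case". For 220 randomised per arm it gives 95% (primary estimand) and 92% (secondary estimand).

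The test itself is defined without a margin. Section 15.2 says: "Individual endpoint analyses are based on treatment comparisons using a 2-sided t-test on a 5% level of significance". Section 15.10 says: "For all 4 endpoints the null hypothesis tested is the hypothesis of equality of placebo and 5-grass mix SLIT-drops treatment group". SAP sections 4.1 and 6.1 likewise set a null hypothesis of no difference in means. RQLQ in the second peak season comes second in the hierarchy, after TCS, and endpoints two to four are tested formally only in sequence; their tests "will be only carried out if all previously tested hypotheses are statistically significant at the 5% level".

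SAP section 6.5 replaces the MCID of 0.16 with 0.10 for the peak season and 0.22 for the entire season. SAP section 7 then gives 98% at 180 per arm against 0.10, but repeats 95% and 92% for the two estimands at 220.

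**The concern.** The power statements for RQLQ refer to a hypothesis, that the difference exceeds the MCID, which the plan never tests. A genuine test of that hypothesis would need far more subjects than the planned equality test, so a figure as high as 93% or 98% cannot be its power on these inputs. It is not the power of the equality test either.

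The quality-of-life claim depends on this test. Protocol section 3.2 says that "in order to make additional claims on QoL, hierarchical testing will be employed on this trial". The sample-size conclusions set the TCS and RQLQ figures side by side under the same word, so RQLQ looks much better powered than the primary endpoint. Someone interpreting a non-significant RQLQ result would set it against a 2% to 7% chance of failure, when the plan's own inputs imply about 20% at 180 per arm.

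The second problem is inside the SAP. It updated one RQLQ figure for the new MCID and left two others as they were in the protocol.

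**Working it through.** **Inputs (protocol 15.2, repeated in SAP 7).** RQLQ difference 0.34; SD 1.15; 180 evaluable or 220 randomised per arm; two-sided 5% t-test; MCID 0.16 (protocol) or 0.10 (SAP, peak season). TCS: difference 1.64, SD 5.5.

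**Standard error of the RQLQ difference**, SD × √(2/n):
- n = 180: 1.15 × √(2/180) = 0.1212
- n = 220: 1.15 × √(2/220) = 0.1096

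**Step 1. Reproduce the stated figures.** P(estimate > MCID) = Φ((0.34 − MCID)/SE) at n = 180:
- MCID 0.16: Φ(0.18/0.1212) = Φ(1.485) = 93.1% (stated 93%)
- MCID 0.10: Φ(0.24/0.1212) = Φ(1.980) = 97.6% (stated 98%)

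Both match. The formula has no critical value, so it is not the power of a test.

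**Step 2. Power of tests at n = 180** (noncentral t, two-sided 5%):

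| Null hypothesis | Power |
|---|---|
| Difference = 0 (the planned test) | 79.9% |
| Difference = 0.16 | 31.6% |
| Difference = 0.10 | 50.6% |

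None gives 93% or 98%. A one-sided 5% equality test gives 87.7%, which does not match either. The same noncentral t calculation for TCS gives 80.5% against the stated 80%, so the TCS figure is a true test power.

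**Step 3. Where the two quantities part.** At n = 180 the smallest significant observed difference is 1.967 × 0.1212 = 0.238. Estimates from 0.16 (or 0.10) up to 0.238 count towards the stated 93% (or 98%) but fail the planned test.

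**Step 4. Size needed.** For the equality test to have 93%, 95% or 98% power would take 272, 299 or 370 evaluable subjects per arm.

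**Step 5. At 220 per arm.** With no dilution of the effect and complete data, the equality test has 87.2%, below both 95% and 92%.

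The documents do not print how discontinuation enters the estimand figures. As an illustration, assume 10% loss per year, so 1 − 0.9² = 19% over two years. If the lack-of-efficacy share (1/10) has no effect under the primary estimand, 1.9% of the effect is lost. If the adverse-event plus lack-of-efficacy share (5.5/10) has none under the secondary, 10.45% is lost. The equality test for RQLQ then has 85.9% and 79.1%. The same assumptions give TCS 86.5% and 79.8%, close to the protocol's own statement: "The power will be 86% for the primary estimand and 80% for the secondary estimand". An assumed variance inflation of 1.1 to 1.2 from imputation lowers RQLQ to 82.5–79.1% (primary) and 75.2–71.5% (secondary).

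**Step 6. The unrevised SAP figures.** P(estimate > MCID) at n = 220:

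| Effect lost | MCID 0.16 | MCID 0.10 |
|---|---|---|
| None | 95.0% | 98.6% |
| 1.9% (assumed, primary) | 94.3% | 98.3% |
| 10.45% (assumed, secondary) | 90.6% | 96.9% |

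The printed 95% and 92% lie near the 0.16 column and well below the 0.10 column. In the protocol the primary-estimand figure rises from 93% at 180 evaluable to 95% at 220 randomised. In the SAP it falls from 98% to 95%, without explanation.

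**The case against.** The strongest counter-argument concerns consequence. The sample size rests on TCS, whose power reproduces. No analysis, decision rule or type I error rate depends on the RQLQ figures, and the last subject's last visit (22 September 2023) preceded the SAP date (27 October 2023), so no design choice is open. The corrected 80% equals what was accepted for the primary endpoint. The MCID also stands in the same sentence as the 93% and 98%, so the reference is not hidden. All of that is true and limits the remedy to text. It does not make the figures right: the documents call them power and speak of testing, and the power of the planned test appears nowhere.

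A second objection is that 87% is not a ceiling for the planned analysis, which is a repeated-measures model with covariates and unequal variances, possibly on a square-root scale. This stands: 87.2% is the value for a simple t-test at SD 1.15 with complete data. The SD also matters. The root mean square of the eight SDs in protocol Table 9 is 1.09, which gives about 84% at 180 and 90% at 220, still short of the stated figures. SD 1.15 is the documents' own choice.

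Third, the dilution is a reconstruction. It gives 94.3% and 90.6% at MCID 0.16, not exactly 95% and 92%. For the secondary estimand it treats all such discontinuers as having no effect, whereas under protocol section 15.11.3 "all diary data (including data collected after discontinuation of trial treatment) will be included". The estimand replacements are therefore illustrative. That the SAP changed one figure and not the others needs no reconstruction.

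**Conclusion.** The concern holds. At 180 per arm, on the documents' own difference, SD and test, the power for RQLQ is 79.9%, not 93% or 98%. Those two figures agree with the probability that the point estimate exceeds the MCID; since no formula is printed, the method is inferred, but it fits at both MCID values. At 220 per arm the simple t-test reaches 87.2% with no dilution and complete data, so 95% and 92% are also too high as power of the planned test. How those two were obtained is not stated, and the SAP did not revise them when the MCID changed.

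These are marginal figures. RQLQ is tested formally only after TCS succeeds. At 220 per arm without dilution, the chance that both are significant is about 77% to 84% for an assumed correlation of 0 to 0.9 between the test statistics. The documents claim no joint power, so this is context and not a further error.

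The fault lies in the stated figures and their label. It should be fixed because it misdescribes the second confirmatory test, but it does not touch the validity of that test.

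**What to change.** In SAP section 7, or as a correction in the trial report since follow-up has ended:

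1. State the RQLQ power of the planned two-sided 5% test of no difference as about 80% (observed case, 180 per arm, difference 0.34, SD 1.15).
2. Relabel 93% and 98% as the probability that the observed difference exceeds an MCID of 0.16 and 0.10 respectively.
3. Recompute the primary and secondary estimand powers at 220 per arm for the planned test, printing the dilution and imputation-variance assumptions, or remove 95% and 92%. If an MCID-exceedance probability is kept for the estimands, recalculate it at 0.10.
4. Optionally, note that the RQLQ figures are marginal and do not include the requirement that TCS be significant first.

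The cost is a text edit. Sample size, test, hierarchy and conduct stay as they are; the stated RQLQ power becomes less favourable.

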4.1 Multiplicity adjustment

The trial product estimand is the primary estimand for all endpoints. The analyses for the primary and for the three key secondary endpoints will be controlled for multiplicity to ensure a family wise type I error rate is no larger than 5%.

The multiplicity will be controlled by employing a hierarchical testing procedure by prespecifying the order of the hypothesis to be tested. For the primary and key secondary endpoints the null hypothesis tested, is the hypothesis no difference between placebo and 5grass mix SLIT-drops treatment group.

The testing order of hypothesis is:

- 1. The primary efficacy analysis of the average daily allergic rhinoconjunctivitis TCS during the 2nd PGPS.
- 2. The key secondary efficacy analysis of average weekly overall RQLQ score during the 2nd PGPS.

Statistical analysis plan	Date:	27-Oct-2023	
Trial ID: SU-G-01	Version:	1.0	
EudraCT No.: 2020-000455-12	Status:	Final	
CONFIDENTIAL	Page:	16 of 47	

- 3. The key secondary efficacy analysis of average daily allergic rhinoconjunctivitis TCS during the 1st PGPS.
- 4. The key secondary efficacy analysis of average weekly overall RQLQ score during the 1st PGPS.

The primary endpoint is the 1st hypothesis in the hierarchy and will be tested on a 5% significance level. The testing of endpoints from the 2nd to the 4th in the hypothesis hierarchy will only be is only carried out formally if all previously tested hypotheses are statistically significant at the 5% level.

Additional endpoints and analyses are supportive in nature, thus they will not be controlled for multiplicity.

5 Analysis sets

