The power calculations were done in two steps. This sample size wasthen evaluated using the estimand framework. The power was calculated for both the primary endpoint (TCS) and the key secondary endpoint (RQLQ). It is expected that the treatment difference in overall RQLQ during peak season is greater than the MCID of 0.10 and during entire season greater than 0.22 (Blaiss et al. 2022).

TCS power calculation

The estimated TCS mean, standard deviation and treatment differences during the peak season from three trials is presented in Table 8. The power calculation is based on a TCS treatment difference of 21% (1.64 in absolute value) and a common standard deviation of 5.5. Under these assumptions, the trial has a power of 80% with the sample size of 180 evaluable subjects. The power is 86% for the primary estimand and 80% for the secondary estimand with the assumption that 10% out of 220 subjects will discontinue the trial, with 4.5% of subjects discontinuing due to AEs and 1% due to lack of efficacy each year.

Trial	Placebo $\mu(\sigma)$	Active $\mu(\sigma)$	Difference absolute (relative)
GT-08 2006	8.44 (5.48)	5.14 (4.06)	3.3 (39%)
P05238	7.74 (6.50)	6.10 (5.09)	1.64 (21%)
P08067	5.73 (5.03)	4.56 (4.60)	1.17 (20%)
Average			2.04

Table 8: Mean and standard deviation of TCS during the peak of a season.

RQLQ power evaluation

The estimated RQLQ mean, standard deviation and treatment differences during the peak season from 3 trials raw data is presented in Table 9 below.

Table 9: Mean and standard deviation of RQLQ during the peak of a season.

Trial	Placebo $\mu(\sigma)$	Active $\mu(\sigma)$	Difference Absolute (relative)
GT-08 2005	1.82 (1.11)	1.37 (0.97)	0.45 (25%)
GT-08 2006	1.48 (1.05)	1.05 (0.91)	0.43 (29%)
P05238	1.73 (1.34)	1.41 (1.12)	0.33 (18%)
P08067	1.73 (1.34)	1.18 (1.08)	0.15 (11%)
Average	0.34		

A common standard deviation of 1.15 has been assumed in the power evaluation. An expected placebo mean is 1.60 and an expected treatment difference is 0.34. With 180 evaluable

Statistical analysis plan
Trial ID: SU-G-01
EudraCT No.: 2020-000455-12
CONFIDENTIAL

subjects per treatment arm, the power of 98% is reached for testing if RQLQ treatment difference is greater than proposed MCID of 0.1. The power is 95% for the primary and 92% secondary estimands for the sample size of 220 subjects with the same discontinuation assumptions as for TCS.

Conclusion

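### The printed RQLQ power (95%, 93%, 98%) matches the chance that the estimate exceeds the MCID, not the power of the planned RQLQ test, and omits the condition that TCS must succeed first

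*Protocol*

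**What the plan says.** Protocol 15.2 opens by invoking the hierarchy: "In this trial, primary and secondary endpoints are tested hierarchically to control the family-wise error rate at 5% level". It then says "Individual endpoint analyses are based on treatment comparisons using a 2-sided t-test on a 5% level of significance".

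For TCS it gives 80% power with 180 evaluable subjects, and for the estimands "The power will be 86% for the primary estimand and 80% for the secondary estimand".

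For RQLQ it assumes a difference of 0.34 and an SD of 1.15. It prints 93% for 180 evaluable subjects per arm, worded as testing whether the difference exceeds an MCID of 0.16. It then adds: "The power will be 95% for the primary and 92% secondary estimands for the sample size of 220 subjects". The Conclusion paragraph repeats these figures.

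SAP section 7 lowers the peak-season MCID to 0.10 and raises the observed-case figure to 98%, but leaves the estimand figures as they were: "The power is 95% for the primary and 92% secondary estimands".

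Protocol 15.10 places RQLQ in the 2nd peak season second, behind TCS in the same season. Tests after the first "will be only carried out if all previously tested hypotheses are statistically significant at the 5% level". On the null it says: "For all 4 endpoints the null hypothesis tested is the hypothesis of equality of placebo and 5-grass mix SLIT-drops treatment group". SAP 4.1 keeps the same order and null, with later endpoints tested "formally if all previously tested hypotheses are statistically significant at the 5% level". Both sections name the trial product estimand as primary for all endpoints.

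**The concern.** Two things do not fit. First, the RQLQ figures are worded around exceeding an MCID, whereas the hierarchy tests RQLQ against no difference. Second, a formal RQLQ claim needs both TCS and RQLQ to be significant. The chance of both cannot exceed the chance of the first, yet 95% is printed for RQLQ beside 86% for TCS.

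The quality-of-life claim is what is at stake. Protocol 3.2 gives it as the reason for putting RQLQ in the hierarchy, and Protocol 1.3 links quality-of-life evidence to the reimbursement request behind the trial. Someone who reads the Conclusion paragraphs without further explanation would take that claim to be safer than the primary endpoint. Under the written testing rule it can never be more likely to succeed.

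**Working it through.** **Inputs from Protocol 15.2 and SAP section 7.** TCS difference 1.64, SD 5.5. RQLQ difference 0.34, SD 1.15. MCID 0.16 (protocol) or 0.10 (SAP, peak season). 180 evaluable and 220 randomised per arm. Two-sided 5%. Yearly discontinuation of 1% for lack of efficacy and 4.5% for adverse events.

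**Assumptions of this check.** Dilution of the mean difference is 2 × 1% = 2% for the primary estimand, because lack-of-efficacy dropouts are imputed from placebo. It is 2 × (1% + 4.5%) = 11% for the secondary estimand. The correlation r between the TCS and RQLQ test statistics is not given, so it is varied.

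**Formulas.** SE = SD × √(2/n). Power of the two-sided 5% test of no difference = Φ(difference/SE − 1.96). Chance that the estimate exceeds the MCID = Φ((difference − MCID)/SE).

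**Step 1: the TCS figures reproduce as test power.**
- 180 per arm: SE = 5.5 × √(2/180) = 0.580; Φ(1.64/0.580 − 1.96) = 80.8% (80.5% with the t distribution). Printed: 80%.
- 220 per arm, 2% dilution: 86.5%. Printed: 86%.
- 220 per arm, 11% dilution: 79.5%. Printed: 80%.

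**Step 2: the RQLQ figures reproduce only as the chance of exceeding the MCID.** SE = 1.15 × √(2/180) = 0.1212 at 180 per arm, and 0.1096 at 220 per arm.
- 180 per arm, MCID 0.16: Φ(0.18/0.1212) = 93.1%. Printed: 93%.
- 220 per arm, MCID 0.16: Φ(0.18/0.1096) = 95.0% (94.3% with 2% dilution). Printed: 95%.
- 180 per arm, MCID 0.10: Φ(0.24/0.1212) = 97.6%. Printed: 98%.
- 220 per arm, MCID 0.16, 11% dilution: 90.3%. Printed: 92%, so close but not exact.

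Test-based readings do not give 93% at 180 per arm. The two-sided 5% test of no difference gives 80.1%, and its one-sided 5% version 87.7%. Against 0.16, a two-sided 5% test gives 31.7% and a one-sided 5% test 43.6%.

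**Step 3: RQLQ test as planned, taken alone.**
- 180 per arm: Φ(0.34/0.1212 − 1.96) = 80.1% (79.9% with the t distribution).
- 220 per arm: Φ(0.34/0.1096 − 1.96) = 87.3%; with 2% dilution 86.0%.

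**Step 4: RQLQ under the hierarchy.** The chance that both tests succeed is Φ₂(Φ⁻¹(p₁), Φ⁻¹(p₂); r), where p₁ is the printed TCS power and p₂ the RQLQ power from step 3.

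| Scenario | p₁ | p₂ | r = 0 | 0.3 | 0.5 | 0.7 | 0.9 |
|---|---|---|---|---|---|---|---|
| Observed cases, 180 per arm | 80% | 80.1% | 64.1% | 66.7% | 68.8% | 71.3% | 75.0% |
| Primary estimand, 220 per arm, 2% dilution | 86% | 86.0% | 73.9% | 75.7% | 77.2% | 79.1% | 82.0% |
| Primary estimand, 220 per arm, RQLQ undiluted | 86% | 87.3% | 75.1% | 76.7% | 78.2% | 80.0% | 82.8% |

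Whatever the correlation, the joint chance cannot exceed 80% in the first row or 86% in the other two.

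**The case against.** The best defence is that section 15.2 announces individual endpoint analyses and names the RQLQ event as a difference greater than 0.16. A stand-alone probability above a joint one contradicts nothing, and no sentence calls 95% the chance of success under the hierarchy. This stands as far as it goes: the missing hierarchy is an omission, not a slip of arithmetic. It does not rescue the figures. They are called power, follow a sentence about two-sided 5% tests, and reappear in the Conclusion without qualification, yet they are not the power of any 5% test tried above.

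A reader might go further and infer that the printed figures are sound test powers that lack only the hierarchy, so that RQLQ power is 82-86% (from 86% and 95%), 74-80% (from 80% and 93%) or 78-80% (from 80% and 98%). The documents do not support that. The inputs describe a different event, so those ranges are not the power of the planned test. Once RQLQ is put on the planned test, its stand-alone power is about equal to that of TCS. The striking contrast of 95% with 86% therefore comes mainly from the MCID measure, not from the omitted hierarchy.

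Two limits also stand. The hierarchy runs on the trial product estimand, so 86% is the ceiling that governs the formal test; 80% belongs to a planning scenario. And TCS set the sample size, with RQLQ only evaluated at that size. The SAP, dated 27-Oct-2023, also follows the last subject's last visit (22-Sep-2023), so no design choice rested on its 98%.

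**Conclusion.** The concern holds as a misdescribed quantity plus an omission. The printed 95%, 93% and 98% match the probability that the estimate exceeds the MCID, and none allows for the hierarchy. For the primary estimand, the chance of a formal RQLQ claim is about 74-82%, which is 13 to 21 points below the printed 95%. For observed cases it is about 64-75%, which is 18 to 29 points below the protocol's 93% and 23 to 34 points below the SAP's 98%.

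These ranges rest on the stated differences and SDs, normal approximations, an assumed correlation of 0 to 0.9, and 2% dilution for the primary estimand. The ceilings of 86% and 80% need no correlation; they follow from the printed TCS power and the testing order. They are limits, not estimates.

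A reader might also infer that the trial is too small or that its error control is weakened. Neither follows: the TCS power reproduces, and the testing order still controls the type I error.

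**What to change.** In Protocol 15.2, SAP section 7 and both Conclusion paragraphs:

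- State RQLQ power as that of the two-sided 5% test of no difference: about 80% at 180 per arm and 86-87% at 220 per arm. Label it as RQLQ taken alone, before allowing for the hierarchy. It should not be called conditional on TCS success, which is a different quantity unless the two tests are independent.
- Add the probability that TCS and RQLQ are both significant, using the sponsor's own TCS-RQLQ correlation from the listed trials or a stated range.
- If 93%, 95% and 98% are kept, describe them as the probability that the estimate exceeds the MCID and give the MCID each refers to. The SAP's retained 95% belongs to 0.16; with 0.10, the same formula at 220 per arm gives about 98% with 2% dilution.
- Use 86% only as a ceiling for the formal RQLQ claim. Writing it in place of 95% beside the MCID wording would attach the limit of one event to another.

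The cost is wording and one short bivariate-normal calculation. Sample size and testing order do not change. The only downside is a less favourable stated RQLQ power.
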